9.7.2. Safety evaluation

All subjects who receive at least one dose of Polyoxidonium will be subjected to the safety analysis.

Safety endpoints will be analysed per infusion and per subject at each individual study visit.

Safety endpoints are listed in Section 9.3.2.

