8. RESEARCH QUESTION AND OBJECTIVES

This PASS aims to collect data on the safety of Polyoxidonium in patients, for whom Polyoxidonium is prescribed in routine practice in accordance with the terms of the marketing authorisation (MA). This study is a part of a Risk Management Plan (RMP).

The primary objective is:

- (a) to assess the frequency of adverse drug reactions
- (b) to estimate the proportion of subjects, who develop signs and symptoms of adverse renal effects associated with the use of Polyoxidonium.

Secondary objective is to evaluate the clinical benefit of Polyoxidonium by evaluating the following variables:

- (a) overall clinical improvement as assessed by investigators and subjects
- (b) mean duration of primary treatment of disease
- (c) mean number of days with fever $>38^{\circ}\text{C}$ and (or) disease symptoms
- (d) change in total and differential white blood cells (WBC) count (blood and urine) from baseline to the end of treatment (if data are available).

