9.2.4. Study visits

It is planned to observe each subject for one cycle of treatment with Polyoxidonium. In accordance with the Summary of Product Characteristics (SmPC), the treatment course consists of 5-10 injections depending on the disease. Thus, study duration for individual subject will take 7-23 days. There will be 5-10 study visits coinciding with routine visits to receive Polyoxidonium injections at the health care centre (see Study flow chart in Table 1). If any visit (scheduled or unscheduled) occurs within 30 days after the last injection of Polyoxidonium as a part of routine practice, information on adverse events will be recorded.

Table 1. Study flow chart

Study procedures	Study visits			
	First injection	Interim visits (3 to 8, depending on indication)	Last injection	Follow-up*
Day	Day 1		Day 7 to 23	
Inclusion/exclusion criteria	X			
Informed consent	X			
Demographic data	X			
Height and weight	X			
Medical history	X			
Physical examination**	X	X	X	
Information about relevant infection, allergic condition, etc.	X	X	X	
Vital signs (blood pressure, heart rate, body temperature)**	X	X	X	
Laboratory tests**	X	X	X	
ECG**	X	X	X	
Other diagnostic procedures**	X	X	X	
Polyoxidonium administration	X	X	X	
Concomitant medications	X	X	X	
Adverse events	X	X	X	X
Investigator's and subject's assessment of tolerability and improvement			X	

*any visit (scheduled or unscheduled) which occurs within 30 days after the last injection of Polyoxidonium as a part of routine clinical practice

**if undertaken as a part of routine clinical practice. Results of laboratory tests, ECG examinations and other diagnostic procedures should be recorded only if performed within 3 days before subject's enrolment and (or) during the study period.

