9.2.5. Study procedures

At the first visit, an investigator will inform a subject about the study (refer to Section 10.2.). If the subject consents to take part in the study and signs the written informed consent form, correspondent entry will be recorded in subject's medical records.

Then, a subject will be assigned a unique identification code, consisting of 4 symbols:

- number of the centre (2 digits),
- number of the subject in the center, by chronological order of selection (2 digits).

The investigator will maintain a subjects' identification list as part of the study file.

Actual assessments undertaken at each visit will be determined by clinical practice (see Study flow chart in Table 1). Subjects will not be administered any investigational medicinal products and/or medical procedures neither undergo any laboratory evaluations, diagnostic or monitoring procedures specifically for the purposes of this study.

Concomitant therapies will be administered at discretion of the investigator in accordance to routine clinical practice. According to the SmPC, Polyoxidonium may be administered as monotherapy or concomitantly with antibiotics, antivirals, antifungals, and antihistamines, bronchiolytics, corticosteroids, beta agonists, and cytostatic agents.

At the last visit (i.e., last injection visit), investigators and subjects will rate the overall tolerance of Polyoxidonium treatment as well as improvement.

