9.3.1. Definition of event of interest

In case of suspected adverse renal effect investigator will be encouraged to apply clinical judgement, to perform diagnostic workup and collect as much data as possible to confirm or reject the diagnosis of renal impairment. The signs and symptoms of renal toxicity, indicative of potential renal impairment include but are not limited to: increased blood concentrations of creatinine, potassium, blood urea nitrogen, urine protein levels, ECG changes, characteristic to elevated potassium levels; symptoms of intoxication, e.g. fatigue, nausea, vomiting.

These data for each subject for whom adverse renal effect is suspected will be reviewed and adjudicated by an independent assessor. This final adjudicated conclusion will be qualified as event of interest (a case of adverse renal effect) or suspicion about renal toxicity will be rejected.

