9.3.2. Safety variables

Safety variables include:

- proportion of subjects with adverse renal effects (as defined in Section 9.3.1)
- proportion of subjects, who experienced any AE;
- proportion of subjects with ADRs;
- proportion of subjects experiencing serious adverse events (SAEs);
- proportion of subjects with serious ADRs;
- severity of AEs;

- number of subjects who discontinued the study and the reasons for drop-outs;
- global assessment of tolerability by investigators: very good (no intolerance reactions), good (occasional intolerance reactions), moderate (frequent intolerance reactions), poor (intolerance reactions after every use);
- global assessment of tolerability by subjects: very good, good, moderate and poor.

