9.9. Limitations of the research methods

Due to limited data concerning the signal of outcome of interest no test hypothesis for this study has been formulated.

The limitations of this study are characteristic to other studies of a similar design (i.e., real life observational studies). Information concerning the potential confounders will be difficult to control.

Because of non-randomized design, absence of blinding and control group selection bias and information bias may occur. To mitigate this risk and ensure that study population represents the source population, investigators and study sites will be selected randomly from the available list of Slovakian immunologists and allergologists. The investigators will be trained and encouraged to enroll all eligible patients consecutively and keep screening logs to document the number of patients invited (refer to Section 9.2).

Some misclassification of outcome variables as well as confounders is possible. A validation is planned which will assess the rate of misclassification and correct the estimates accordingly. To mitigate the risk of information bias, investigators encouraged to collect as much data concerning the event of interest (adverse renal effects) as possible within the frame of routine practice. A set of available clinical data about the event of interest, presented in a standard format, will be adjudicated by an independent assessor.

Misclassification of exposure is not expected to happen. However due to nature of dosing regimen study population may be not homogenous in terms of duration of treatment and dosing schedule.

Since inclusion and exclusion criteria are very limited, it is expected that enrolled subjects will represent the source population (i.e., target patients of Polyoxidonium therapy) in Slovakia. To document the number of patients invited and assess selection bias in subject recruitment, screening logs will be used.

Subjects included in the study are expected to be representative of the source population (i.e., patients for whom Polyoxidonium is routinely prescribed in Slovakia) in terms of gender, age distribution, socio-economic class, indication, concomitant diseases.

Confounding by known and unknown covariates may happen:

- Patients with variety of diseases and medical conditions are planned to enroll in scope with Polyoxidonium approved indications. Study population will not be homogenous.

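### The primary renal proportion counts every never-suspected subject as event-free, and no data collection the protocol describes supports the promised misclassification correction

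*Protocol*

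**What the plan says.** Section 8 makes it a primary objective "to estimate the proportion of subjects, who develop signs and symptoms of adverse renal effects associated with the use of Polyoxidonium". Section 9.3.2 lists that proportion first among the safety variables and refers to section 9.3.1 for the definition. Section 9.7.2 sets the denominator for safety endpoints: "All subjects who receive at least one dose of Polyoxidonium will be subjected to the safety analysis". No renal assessment is required for a subject to be counted. By contrast, section 9.7.3 admits subjects to the benefit analysis only if their benefit data are available.

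Section 9.3.1 fixes the numerator. Its indicative signs are raised creatinine, potassium, blood urea nitrogen and urine protein, certain ECG changes, and symptoms such as fatigue, nausea and vomiting. The route to a case runs through suspicion: "These data for each subject for whom adverse renal effect is suspected will be reviewed and adjudicated by an independent assessor".

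On testing, section 9.2.5 says subjects will not "neither undergo any laboratory evaluations, diagnostic or monitoring procedures specifically for the purposes of this study". The footnotes to Table 1 in section 9.2.4 limit laboratory tests to those done "if undertaken as a part of routine clinical practice". Results from before enrolment "should be recorded only if performed within 3 days before" it; results during the study period are also recorded.

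Section 9.9 states: "A validation is planned which will assess the rate of misclassification and correct the estimates accordingly". It gives no sample, reference standard or procedure for this. It adds that the potential for missing data in this setting is unknown.

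**The concern.** Numerator and denominator rest on different information. The denominator is everyone dosed. The numerator can contain only subjects in whom someone first thought of the kidney. Adjudication can remove false positives from that group, but it cannot find cases outside it. Two kinds of subject are therefore counted as event-free without evidence: those neither tested nor suspected, and those whose routine result was abnormal but raised no suspicion.

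This matters because the signal behind the study, described in section 7.2, includes raised creatinine and urea in dogs, and such changes can be silent. Section 9.1 says the study may supply evidence that risks are absent. Under-detection leads toward that conclusion. A report of no cases in 500 could mean no cases among the much smaller number in whom a silent case could have been seen, and the promised correction would suggest that this had been dealt with.

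**Working it through.** **Inputs from the protocol.** Planned size 500 (section 9.5). Denominator all dosed (9.7.2). Cases only through suspicion and adjudication (9.3.1). No study-mandated tests (9.2.5). Section 9.5 reports no sample-size calculation and gives no rate or precision, so there is no stated figure to reproduce.

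**Assumptions.** The share of subjects with a usable renal test is not given; 20%, 50% and 80% are used. The true risk is set at 1%. All events are taken to be silent, so that only a test reveals them, and every event in a tested subject is taken to be suspected and confirmed.

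**Step 1: attenuation.** With tested share *s* and true risk *p*, the expected reported proportion over all dosed is *s* × *p*, for example 0.2 × 1% = 0.2%. The chance of at least one reported case is 1 − (1 − *sp*)^500.

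**Step 2: zero events.** The exact two-sided 95% upper limit for 0 of *n* is 1 − 0.025^(1/*n*).

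| Tested share (assumed) | Tested *n* | Expected reported proportion over 500 | Chance of at least one reported case | Upper limit for 0 of tested *n* |
|---|---|---|---|---|
| 20% | 100 | 0.2% | 63.2% | 3.62% |
| 50% | 250 | 0.5% | 91.8% | 1.46% |
| 80% | 400 | 0.8% | 98.2% | 0.92% |
| 100% | 500 | 1.0% | 99.3% | 0.74% |

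The 0.74% is this review's calculation for 0 of 500; the protocol prints no such limit.

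**Step 3: what adjudication can estimate.** Reviewing suspected cases gives confirmed / suspected, a positive predictive value. Sensitivity is confirmed / (confirmed + missed), and the missed cases are not reviewed. With specificity taken as 1, a corrected proportion is observed / sensitivity. Suppose 2 cases are confirmed, so the observed value is 2/500 = 0.4%:

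- sensitivity 0.8: 0.4% / 0.8 = 0.5%
- sensitivity 0.5: 0.4% / 0.5 = 0.8%
- sensitivity 0.2: 0.4% / 0.2 = 2.0%

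Nothing in the described adjudication chooses among these.

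**Step 4: do the two denominators bound the truth?** Take the same 2 cases, both in tested subjects, with 250 tested and correctly classified. The all-dosed and tested-subject figures are 2/500 = 0.4% and 2/250 = 0.8%. Without any assumption about the 250 untested, the possible range is 2/500 to (2 + 250)/500, or 0.4% to 50.4%. The pair 0.4% and 0.8% is therefore not a bound on the true proportion.

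**The case against.** An all-dosed safety set is conventional, and a supplementary denominator is ordinary SAP material. The study is exploratory and descriptive, and section 9.9 already concedes misclassification, information bias and missing data of unknown extent. This stands as far as the denominator alone is concerned. It does not reach the suspicion trigger in 9.3.1 or the correction promise in 9.9, which are protocol text. Nor does section 9.9 say that never-suspected subjects are counted as non-events.

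Several stronger readings are tempting but unsupported:

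- **That every untested subject counts as event-free.** Symptoms or ECG changes can raise suspicion under 9.3.1, which then encourages a workup, and 11.2 has general questions about well-being asked at all visits. An untested subject can become suspected, tested and counted. The gap concerns those never suspected.
- **That an abnormal routine value is lost entirely.** Section 9.3 records routine results, and the adverse event definition in 11.1.1 includes abnormal laboratory findings. What is missing is a rule that takes such a value to the assessor when nobody suspects a renal effect.
- **That no correction could ever be computed.** Section 9.9 does not confine the validation to suspected cases. Routine results in tested but unsuspected subjects could support a partial correction if testing were unrelated to risk. The supportable statement is that no data collection described in the protocol provides for it.
- **That the 3-day limit also pushes the estimate toward zero.** It can work either way: without an earlier value, long-standing impairment may look new.
- **That the attenuation figures are expected values for this trial.** They assume all events are silent, whereas the objective covers signs and symptoms, and the tested shares have no source in the protocol.

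**Conclusion.** The point holds in this form: the primary renal proportion is biased toward zero for silent events, because never-suspected subjects enter an all-dosed denominator as non-events, and the verification described yields no sensitivity with which to correct it. The direction follows from sections 9.2.5, 9.3.1, 9.3.2 and 9.7.2 read together; no single sentence spells out the fraction. The size depends on the tested share and on the share of events that are silent, and the protocol gives neither. Over the assumed range, a 1% risk would be reported at a fifth to four fifths of its value. A result of no cases would look about five times as reassuring as the tested subjects justify at 20% tested (3.62 / 0.74 = 4.9), and about 1.2 times at 80% (0.92 / 0.74). Events that cause symptoms and prompt a workup reduce the bias. Because this is a primary estimate and the repair is cheap, the protocol should be changed.

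**What to change.** 1. **Section 9.3.1:** have the eCRF flag every recorded on-study renal value above the laboratory's limit, or clearly above an available baseline, and send it to the planned assessor whether or not the investigator suspects a renal effect.
2. **Section 9.7.2:** keep the all-dosed proportion. Beside it, report the number of subjects with at least one renal test after the first injection, and the renal proportion among them, with and without a baseline value. State that the two proportions do not bound the true risk, because testing may depend on risk.
3. **Section 9.9:** delete the clause on correcting the estimates, or limit it to the positive predictive value, unless the validation is specified to cover records of unsuspected subjects as well.
4. **Optional, sections 9.2.4 and 9.3:** transcribe the latest earlier renal values on file, with their dates, to separate pre-existing from new abnormalities.

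The cost is protocol and SAP wording, a few eCRF fields, more cases for the assessor, and a wider interval for the tested-subject figure. No test is added, so the study stays non-interventional.

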9.7.3. Clinical benefit evaluation

All subjects who receive at least one dose of Polyoxidonium and for whom the clinical benefit variables are available at the end of study will be included in clinical benefit analyses.

Clinical benefit endpoints are listed in Section 9.3.3.

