9.2.3. Subject withdrawal criteria

Subject participation in the study must be prematurely discontinued for any of the following reasons:

- subject withdraws his/her consent;
- subject stops the treatment with Polyoxidonium;
- occurrence of AE or intercurrent condition that require discontinuation of treatment with Polyoxidonium;
- subject is lost to follow-up.
- subject has a confirmed positive serum or urine pregnancy test. Subjects with positive pregnancy tests will be followed to resolution (either miscarriage or normal birth, with or without complications). Refer to Section 11.5.

The reasons for study discontinuation must be recorded in a subject's medical records and eCRF.

A subject that discontinues from the study will not be replaced.

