9.3.3. Clinical benefit variables

Clinical benefit assessment includes the following variables:

- global assessment of improvement by subjects score (0 to 4 scale: 0=much worse; 1= somewhat worse; 2=same; 3=somewhat improved; 4 = greatly improved)
- global assessment of improvement by investigators score (0 to 5 scale: 0 = worse; 1 = no appreciable improvement; 2 = slight improvement; 3 = moderate improvement; 4 = marked improvement; 5 = complete resolution)
- mean duration of primary treatment of disease (i.e., days with antibiotic use in case of infection or antiallergic medication in case of allergies),
- days with fever $>38^{\circ}\text{C}$ /days with symptoms,
- total and differential WBC count in blood and urine (if data are available).

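### Improvement and tolerability are rated only at the last-injection visit, so subjects who stop treatment early have no scheduled rating and are missing from both summaries

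*Protocol*

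**What the plan says.** On timing, Protocol 9.2.5 states: "At the last visit (i.e., last injection visit), investigators and subjects will rate the overall tolerance of Polyoxidonium treatment as well as improvement". Table 1 agrees: the rating row is marked only in the last-injection column, which is dated Day 7 to Day 23.

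On early stopping, 9.2.3 ends participation when the "subject stops the treatment with Polyoxidonium" and on "occurrence of AE or intercurrent condition that require discontinuation of treatment with Polyoxidonium". It adds: "A subject that discontinues from the study will not be replaced".

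On analysis sets, 9.7.3 takes subjects with at least one dose "for whom the clinical benefit variables are available at the end of study will be included in clinical benefit analyses". Tolerability is listed among the safety variables in 9.3.2, so it falls under 9.7.2: "All subjects who receive at least one dose of Polyoxidonium will be subjected to the safety analysis".

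On durations, 9.3.3 includes "mean duration of primary treatment of disease (i.e., days with antibiotic use in case of infection or antiallergic medication in case of allergies") and days with fever or symptoms. Section 9.2.4 gives the window: "Thus, study duration for individual subject will take 7-23 days". In Table 1, concomitant medication and disease information carry no follow-up mark. Adverse events are the only item collected after the last injection.

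**The concern.** The subjects most likely to miss the ratings are those who stopped because of intolerance, an adverse event or lack of effect. A summary confined to rated subjects then describes people who finished the course, not people who were treated. Tolerability matters more than its place among the global scores suggests, because it is a safety variable in a safety study. Its worst grade describes a reaction at every use, and a subject with that experience is a natural candidate for stopping early.

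The gap is one of data collection. Section 9.7 has the SAP issued before database lock, and a SAP at that stage cannot recover ratings that were never taken.

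A smaller, related matter concerns the duration variables. Their observation window closes at the last injection and differs by regimen.

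**Working it through.** **1. Which subjects have a scheduled rating**

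| Subject | Status under 9.2.3 | Rating in 9.2.5 / Table 1 | Improvement (9.7.3) | Tolerability (9.7.2) |
|---|---|---|---|---|
| Completes the course | Stays in | At last injection | Included | Included |
| Stops early, any reason | Withdrawn, not replaced | None scheduled | Excluded if no data at end of study | In the set, but no value |

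Improvement loses early stoppers through the definition of the analysis set. Tolerability loses them through the visit schedule.

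**2. Size for the improvement rating**

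The protocol gives no dropout rate and no response rate, so these inputs are assumptions. Let p be the proportion improved among rated subjects (0.80), d the proportion unrated, and q the proportion improved among the unrated.

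All-treated proportion = (1 − d)p + dq. Overstatement = p − [(1 − d)p + dq] = d(p − q).

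- d = 0.05, q = 0.20 to 0.40: 0.76 + 0.01 to 0.02 = 77-78%; overstatement 2-3 points.
- d = 0.10, q = 0.20 to 0.40: 0.72 + 0.02 to 0.04 = 74-76%; overstatement 4-6 points.
- d = 0.20, q = 0.20 to 0.40: 0.64 + 0.04 to 0.08 = 68-72%; overstatement 8-12 points.
- q = 0.95 (most stopped because they had recovered): 81.5% at d = 0.10 and 83% at d = 0.20, so the reported 80% is too low by 1.5 and 3 points.

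With no assumption about q, the bounds are (1 − d)p and (1 − d)p + d: 72-82% at d = 0.10 and 64-84% at d = 0.20. For the planned 500 subjects, d = 0.10 means 450 rated and 50 unrated.

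**3. Observation window for the durations**

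The regimens in 9.2.6 were laid out with the first injection on Day 1:

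- Acute, 5 injections: 1, 2, 3, 5, 7. Ends Day 7.
- Allergic, 5 injections: 1, 2, 4, 6, 8. Ends Day 8.
- Acute, 10 injections: 1, 2, 3, then seven steps of 2. Ends Day 17.
- Urogenital or herpes, 10 injections: 1 + 9 × 2. Ends Day 19.
- Chronic, 10 injections: the fifth falls on Day 9 (1 + 4 × 2), then five more twice weekly. With all gaps of 3 days it ends Day 24. With gaps 3, 4, 3, 4, 3 it ends Day 26, and with gaps 4, 3, 4, 3, 4 Day 27.

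The lower limit of 7 days in 9.2.4 is reproduced. The upper limit of 23 is not, because the chronic regimen as written runs past it.

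A duration cut at the last visit cannot exceed the true one. If ongoing treatment or symptoms were averaged as complete, the mean would be biased short, and the shortfall would depend on the length of the course.

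**The case against.** Four points on the other side carry weight.

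- **Early stoppers are not expressly left unrated.** Section 11.2 mentions a completion/discontinuation visit, and the last-injection visit could be read as the last injection actually received. However, Table 1 has no discontinuation column and 11.2 attaches no rating to that visit. A subject who decides to stop after leaving the clinic had an injection that nobody knew was the last. The text leaves the gap open.
- **Discontinuations are not hidden.** Section 9.3.2 lists their number and reasons, and 9.2.3 requires the reason in the eCRF. This stands. It shows how many left, but not how they would have rated.
- **Ongoing durations can be handled in the SAP.** Section 9.3 records start and stop dates or marks a medication as continuing, and 9.7.1 plans medians and percentiles as well as means. This largely stands, and it is why durations are only a secondary point. The protocol does not say that ongoing durations will be averaged as complete.
- **The consequence is limited.** Benefit is a secondary objective in an exploratory, descriptive study. Adverse drug reaction frequency and renal effects do not depend on these ratings.

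A reader might also infer three stronger things that the documents do not support:

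- That 9.7.3 governs tolerability. It does not; 9.7.2 does.
- That schedule length alone creates a two- to three-fold difference in mean treatment duration. That starts the clock at the first injection, whereas 9.3 also records earlier medication with start dates.
- That the objective should be renamed because there is no control group. Sections 9.1 and 9.9 declare the uncontrolled design and its limits, so the label is a matter of preference.

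**Conclusion.** The point holds for the ratings. The protocol schedules them only at the last injection, withdraws early stoppers without one, and limits the improvement analysis to subjects with end-of-study data. Tolerability has the same gap in practice, despite its all-treated set.

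Overstatement is likely but not certain. Under the assumed 80% improved among rated subjects and 20-40% among the unrated, it is 4-6 points at 10% unrated and 8-12 points at 20%. It disappears if the two groups respond alike, and it turns slightly negative if subjects mostly stop because they have recovered. The actual size cannot be computed, because no dropout rate is given. It would be wrong to conclude that the results must favour the drug.

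For durations, the direction of any truncation bias is certain wherever ongoing episodes are counted as complete. The protocol does not fix that treatment, and no size is claimed here. Separately, the 7-23 day window in 9.2.4 and the chronic regimen in 9.2.6 disagree and must be reconciled; no view is taken on which is right.

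**What to change.** 1. In 9.2.5 and Table 1, take both global ratings at the last injection or, for a subject who stops early, at the contact where stopping is recorded. This adds no laboratory or diagnostic procedure.
2. In 9.7.3, report improvement over all subjects with at least one dose. Show the unrated as their own category with reasons, and add a sensitivity analysis counting them as not improved.
3. In the tolerability table, give subjects who stopped for an adverse event a separate line.
4. State that treatment or symptoms still ongoing at the last visit are censored there. This can go in the SAP.
5. Reconcile the individual study duration in 9.2.4 and Table 1 with the regimens in 9.2.6.

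The cost is protocol and SAP wording, one eCRF form enabled at early stop, and possibly slightly less favourable figures.
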